2.4.2 Exclusion Criteria

Patients will be excluded from study entry if they meet any of the following exclusion criteria:

1. Patients who have a creatinine greater than or equal to 2mg/dL or estimated creatinine clearance less than 40 mL/min or those requiring hemodialysis.
2. Patients who have been diagnosed with active TMA, defined as meeting all the following criteria:
 - Greater than 4% schistocytes in blood (or equivalent if semiquantitative scale is used e.g., 3+ or 4+ schistocytes on peripheral blood smear)
 - De novo, prolonged or progressive thrombocytopenia (platelet count less than $50 \times 10^9/L$ or 50% or greater reduction from previous counts)
 - Sudden and persistent increase in lactate dehydrogenase concentration greater than 2x ULN
 - Decrease in hemoglobin concentration or increased transfusion requirement attributed to Coombs-negative hemolysis
 - Decrease in serum haptoglobin
3. Patients who have previously received treatment with eculizumab.
4. Patients who have previously received checkpoint inhibitors (either before or after allo-HCT).
5. Patients who have been diagnosed with overlap syndrome, that is, with any concurrent features of cGVHD.
6. Patients requiring mechanical ventilation or vasopressor support.
7. Patients who have received any systemic treatment, besides steroids, as upfront treatment of aGVHD or as treatment for SR-aGVHD. Reinstitution of previously used GVHD prophylaxis agents (e.g., tacrolimus, cyclosporin, MTX, MMF) or substitutes in cases with previously documented intolerance will be permitted. Previous treatment with a JAK inhibitor as part of GVHD prophylaxis or treatment is not allowed.
8. Patients who have severe hypoalbuminemia, with an albumin of less than or equal to 1 g/dl.
9. Patients who have a creatine kinase (CK) level of greater than 5 times the upper limit of normal.
10. Patients with uncontrolled infections. Infections are considered controlled if appropriate therapy has been instituted and, at the time of enrollment, no signs of progression are present. Persisting fever without other signs or symptoms will not be interpreted as progressing infection. Progression of infection is defined as:
 - hemodynamic instability attributable to sepsis **OR**
 - new symptoms attributable to infection **OR**
 - worsening physical signs attributable to infection **OR**
 - worsening radiographic findings attributable to infection

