
Myalgia and serum CK-elevation:

There is an association of myositis with Ricin-based toxicity. Therefore, participants should be monitored for signs of myositis. If participants experience muscle pain, then a serum CK should be performed. The next dosage of T-Guard should be withheld in case of a CK elevation greater than 5 times ULN. Dosing can resume if the CK decreases to less than or equal to 5 ULN and symptoms of myositis has improved to Grade 2 or less by CTCAE v.5. Dosing can proceed at the investigator's discretion if deemed in the best interest of the participant.

Other toxicities:

Participants with another non-hematologic grade 3 or higher toxicity which is not attributable to an expected post-transplant event may have their study drug held at the attending physician's discretion. Expected post-transplant events include steroid-related toxicity and chemotherapy toxicity. T-Guard should be restarted after recovery of related toxicities to grade 2 or lower or identification of an alternative cause for these toxicities.

Infection:

Participants with severe infections resulting in hemodynamic instability requiring use of vasopressor medication may have study drug held at the discretion of the treating physician.

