4.2.1 Treatment

Treatment should be initiated as soon as possible after randomization, ideally within 24 hours. A maximum of 72 hours (3 days) after randomization is allowable.

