4.3 STUDY MONITORING

4.3.1 Follow-up Schedule

The Follow-up Schedule for scheduled study visits is outlined in [Table 4-1](#).

The timing of follow-up visits is based on the date of randomization (Day 0). A detailed description of each of the forms and the procedures required for forms completion and submission can be found in the Data Management Handbook and User's Guide.

Table 4-1: Follow-up Schedule

Assessment Time	Target Day (Days Post- Randomization)
1 week	6 days ¹
2 weeks	14 days ²
3 weeks	21 days ²
4 weeks	28 days [#]
5 weeks	35 days ²
6 weeks	42 days ²
7 weeks	49 days ²
8 weeks	56 days ²
10 weeks	70 days ³
90 days	90 days ³
6 months	180 days ⁴

¹Target day window for Ruxolitinib arm only is +/-3 days (see section [2.5.1.5](#) for guidance on T-Guard infusion delays)

²Target day window is +/- 3 days

³Target window is +/-14 days

⁴Target window is +/-28 days

[#]Target day window is +/-2 days

Data Collection: The investigator or site designee will enter data collected using an electronic data capture system. In the interest of collecting data in the most efficient manner, the investigator or site designee should transcribe data (including laboratory values, if applicable) in the eCRF in a timely manner after the participant visit unless otherwise noted. The BMT CTN DCC will be reviewing form submission regularly and will follow-up to assure data is submitted promptly.

The investigator or site designee is responsible for ensuring that all data in the eCRFs and queries are accurate and complete and that all entries are verifiable with source documents. These documents should be appropriately maintained by the site.

The monitor will verify a subset of the data in the eCRFs with source documents and confirm that there are no inconsistencies between them.

Criteria for Forms Submission: Criteria for timeliness of submission for all study forms are detailed in the Data Management Handbook and User's Guide. Forms that are not entered in the EDC system within the specified time will be considered delinquent. Transplant Centers can view past due forms via the EDC system. A missing form will continue to appear until the form is entered into the EDC system, or until an exception is granted and entered into the Missing Form Exception File, as detailed in the Data Management Handbook and User's Guide.

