10. Peripheral blood* and urine sample* for GVHD biomarker testing (See APPENDIX B)

T-Guard Treatment Assessments

The assessments listed below are to be completed on days of treatment for participants randomized to receive T-Guard. Assessments should be done prior to infusion, unless otherwise specified.

1. Complete aGVHD staging and grading information including assessments of rash, diarrhea, nausea/vomiting, and bilirubin on Days of infusion
2. Vital signs (temperature, pulse, respiratory rate, blood pressure) on Days of infusion . Vital signs should be taken just before starting the infusion, 15 and 30 minutes after the start of the infusion, then every 30 minutes during the infusion, and at 1 hour post-infusion. Deviation of +/- 5 minutes may occur for all vital sign collection timepoints.
3. Albumin on Days of infusion
4. CBC with differential and platelet count on Days of infusion

5. Renal function (blood urea and/or blood urea nitrogen, creatinine) on Day of 4th infusion
6. Schistocytes, haptoglobin and LDH on Day of 4th infusion
7. Peripheral blood for EBV and CMV viral load on Day of 4th infusion
8. Recording and review of Concomitant medications on Days of infusions
 - a. For all immunosuppressant agents, the overall start and stop date will be captured. For agents where dosing is tapered in response to drug levels, the medication dosing will not require reporting.
 - b. Dosing for corticosteroids will be captured for all dosing changes.
9. Recording of AE/SAEs as described in Section 4.4 Adverse Event Reporting
10. Recording of infections
11. Peripheral blood* for humoral response (ADA) on Day of 4th infusion (See APPENDIX B)
12. Peripheral blood* for PK at the following timepoints (See APPENDIX B):
 - a. 1st infusion: pre-infusion and at 4, 5, 6, 8, and 24 hours after start of infusion
 - b. 2nd infusion: pre-infusion and at 4 and 24 hours after start of infusion
 - c. 3rd infusion: pre-infusion and at 4 and 24 hours after start of infusion
 - d. 4th infusion: pre-infusion and at 4, 6, 24, and 48 hours after start of infusion

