Pre-infusion samples should be drawn prior to T-Guard administration. A window of +/- 15 minutes is allowed for samples drawn at 4 hours after the start of infusion, a window of +/-30 minutes for the sample drawn 5, 6, or 8 hours after the start of infusion, and a window of +/- 1 hour for samples drawn 24 or 48 hours after the start of infusion. Every effort should be made to collect PK samples at all timepoints; however, *no* PK sampling is required on weekend days. Please refer to Section 2.5.1.5 for more information regarding T-Guard infusion delays.

Post-Randomization Assessments

The following assessments and observations must be completed at the timepoints designated below.

1. Complete aGVHD staging and grading information including assessments of rash, diarrhea, nausea/vomiting, and bilirubin at Days 0, 6, 14, 21, 28, 35, 42, 49, 56, 70, 90, and 180
2. cGVHD evaluation (if present) Day 28, 56, 90, and 180
3. Blood pressure at Days 0, 6, 14, 21, 28, 35, 42, 49, 56, 70, 90, and 180
4. Albumin at Days 0, 6, 28, 56, 90, and 180
5. CBC with differential and platelets at Days 0, 6, 14, 21, 28, 56, 90, and 180
6. Renal function (blood urea and/or blood urea nitrogen, creatinine) on Days 6, 14, 21 and 28
7. Schistocytes, haptoglobin and LDH on Days 6, 14, 21 and 28
8. Karnofsky performance status at Days 28, 56, 90, and 180
9. Peripheral blood for EBV and CMV viral load at Days 6, 14, 21, 28, 35, 42, 49, 56 and 180
10. Recording and review of Concomitant medications other than immunosuppressant agents will be collected starting at 7 days prior to randomization through 30 days post-last treatment dose for T-Guard and through Day 44 for ruxolitinib. Recording of all systemic immune suppressive therapy (as appropriate: tacrolimus, cyclosporine, etc.), as well as topical agents, and all anti-infectives used for prophylaxis or treatment at Days 6,

14, 21, 28, 35, 42, 49, 56, 70, 90, and 180

- a. For all immunosuppressant agents, the overall start and stop date will be captured. For agents where dosing is tapered in response to drug levels, the medication dosing will not require reporting.
- b. Dosing for corticosteroids will be captured for all dosing changes.

11. Patient reported outcomes at Days 28, 90 and 180 (see APPENDIX E)

12. Recording of toxicities on Days 56, 70, 90, and 180

13. Recording of AE/SAEs as described in Section 4.4 Adverse Event Reporting

14. Recording of infections through Day 180

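### T-Guard arm: creatinine, LDH, haptoglobin and schistocytes need not be repeated until the 4th infusion, and CK has no scheduled test after screening

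*Combined protocol and SAP*

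**What the plan says.** Section 2.5.1.4 plans T-Guard at 4 mg/m² on Days 0, 2, 4 and 6. Section 4.3.2 places creatinine, LDH, haptoglobin, schistocytes, albumin and CK in the 24 to 72 hours before enrollment. Its T-Guard treatment list, which is pre-infusion unless stated otherwise, then has "Schistocytes, haptoglobin and LDH on Day of 4th infusion", with renal function on the same day, but "Albumin on Days of infusion". CBC with platelets, vital signs and aGVHD staging with bilirubin are also required at each infusion. The post-randomization list has "Schistocytes, haptoglobin and LDH on Days 6, 14, 21 and 28", and renal function on the same days. On schedule, Day 6 is the day of the 4th infusion.

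CK appears in three roles. Section 2.4.2 excludes "Patients who have a creatine kinase (CK) level of greater than 5 times the upper limit of normal". Section 2.5.1.6 states: "The next dosage of T-Guard should be withheld in case of a CK elevation greater than 5 times ULN". Section 4.4.4 makes CK elevation of any grade an event of special interest, reportable within 24 hours. The only instruction to measure CK after screening is in Section 2.5.1.6, repeated in footnote 5 of Table K-1: "If participants experience muscle pain, then a serum CK should be performed".

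**The concern.** The protocol itself names the hazards that these tests track. Section 1.3.1.2.3 counts thrombotic microangiopathy (TMA) among the possibly drug-related effects seen in more than one patient, and says that myalgia with ricin A-chain immunotoxins often comes with a CK rise. Section 1.3.1.2.1 mentions rhabdomyolysis as a known severe toxicity of the class. Section 1.3.1.2.4 lists renal dysfunction and active or suspected TMA among the risk features of the three early deaths in the previous study, and responds with LDH-based screening at entry.

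After entry, the plan requires no repeat of those markers until most of the drug has been given. Section 2.5.1.4 already calls for dosing to be delayed when toxicity occurs. A change after dose 1 or 2 could be known before a later dose, but only if someone has measured it. For CK, the plan has a numerical hold rule and a reporting duty but no scheduled measurement to feed them.

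**Working it through.** No stated figure needs reproducing. The check sets the schedule beside the dosing days and counts.

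**Inputs.** Screening window: Day -3 to Day -1 (Section 4.3.2). Infusions: Days 0, 2, 4 and 6, 4 mg/m² each (2.5.1.4). Latest start: "A maximum of 72 hours (3 days) after randomization is allowable" (4.2.1). Participants per arm: 246 / 2 = 123 (5.1).

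**Gap on schedule.** Shortest: 6 - (-1) = 7 days. Longest: 6 - (-3) = 9 days.

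**Doses before the repeat.** Days 0, 2 and 4 precede the Day 6 panel: 3 of 4 doses, or 3 × 4 = 12 of 4 × 4 = 16 mg/m².

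**Latest start.** With dose 1 on Day 3, the 4th infusion falls on Day 3 + 6 = 9. If the panel travels with that infusion, the gap is 9 - (-1) = 10 to 9 - (-3) = 12 days, still with 3 of 4 doses given. This assumes no further delay between doses.

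**Tests compared.**

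| Test | Entry criterion (2.4.2) | Specific T-Guard hold (2.5.1.6) | Infusions with a required value |
|---|---|---|---|
| Albumin | yes, at or below 1 g/dL | yes, same limit | 1, 2, 3, 4 |
| CK | yes, above 5 × ULN | yes, same limit | none without muscle pain |
| Creatinine | yes | none | 4 |
| LDH, haptoglobin, schistocytes | yes, within the TMA definition | none | 4 |

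Albumin and CK have the same two roles. Required values at the four infusions are 4 for albumin and 0 for CK in a participant without muscle pain.

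**Past events.** Table 1-2 shows microangiopathy in 1 (Grade 2) + 1 (Grade 3) = 2 of 20 Phase 1/2 patients, treated before the current TMA exclusion. Timing relative to dose is not given. Table 1-1 shows muscular weakness in 5 of 20 and myopathy in 5 of 20. Weakness without pain would not require a CK. Steroids also cause myopathy (1.2.1), so these counts cannot be attributed to T-Guard.

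The columns of Table K-1 are not legible in the text version and are not relied on.

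**The case against.** The case for leaving the schedule alone has substance.

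- **Existing cover.** The lists are minimums. Platelets and hemoglobin, two elements of the TMA definition, are checked at each infusion. Inpatient dosing is strongly recommended, and close drug-level monitoring of prophylaxis agents, adjusted for renal toxicity (2.5.3.1), makes a week without creatinine unlikely in practice. This stands: detection is reduced, not absent. But low and falling platelets were common in Phase 1/2, so a platelet fall alone separates TMA poorly from other causes.
- **The CK rule is coherent.** CK rises are described as accompanying myalgia, sites must watch for signs of myositis, and harm from a painless rise is not documented. A reader might infer that the hold cannot act on a painless rise at all. That goes too far: it can act on any CK obtained, but none is required.
- **No defined action.** There is no T-Guard hold rule for creatinine or hemolysis markers, and the clause on other toxicities is discretionary and limited to non-hematologic Grade 3 or higher. This stands. The added panels would inform the general delay for toxicity, and would not by themselves establish TMA, which also needs Coombs-negative hemolysis and a persistent LDH rise.
- **The early deaths.** A reader might infer a failure of on-treatment monitoring. Section 1.3.1.2.4 describes features present at the start of treatment, which the entry criteria now address.
- **Late starts.** Because Section 4.3.1 dates visits from randomization, a reader might infer that a late starter's Day 6 panel comes after only 2 of 4 doses, and that such a participant has five panels through Day 28 against four on ruxolitinib. The documents do not support this securely. Footnote 1 of Table 4-1 limits the Day 6 window to the ruxolitinib arm and refers T-Guard to Section 2.5.1.5, which keeps assessments with the delayed infusion. Appendix B and footnote 9 of Table K-1 place T-Guard Day 6 research samples just before the 4th infusion. No text settles this for LDH or creatinine, and nothing here depends on it.

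**Conclusion.** The gap is real and follows from the text. On the planned schedule, 3 of 4 doses precede the next required creatinine, LDH, haptoglobin or schistocyte result, 7 to 9 days after screening. The gap is up to 12 days with a 72-hour late start if the panel moves with infusion 4. CK has no scheduled test after screening, although the plan holds doses on it. The contrast with albumin is not explained.

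The benefit cannot be quantified, because the timing of past TMA events is not reported and local practice may already exceed the minimum. The point does not affect the validity of the primary analysis. It is a cheap safety improvement that the sponsor should make, aimed at hazards that the protocol names.

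**What to change.** In the T-Guard treatment list of Section 4.3.2, with Appendix K to match, add to the pre-infusion blood already drawn for CBC and albumin:

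- CK at infusions 2, 3 and 4;
- creatinine, LDH, haptoglobin and schistocytes at infusions 2 and 3.

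Results feed the existing CK hold (2.5.1.6) and the general delay for toxicity (2.5.1.4). No new threshold is needed, and a result that arrives after an infusion informs the next one.

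To keep ascertainment equal, state that the TMA comparison in Section 5.8.7 uses the Day 6, 14, 21 and 28 assessments that Section 3.5.1.7 already names, with its blinded review. Report abnormalities found only on the extra T-Guard tests descriptively, outside the between-arm Grade 3-5 comparison in Section 5.6.12.

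Cost: at most 2 × 123 = 246 panels and 3 × 123 = 369 CK tests, with no new visit. Some asymptomatic CK rises will delay a dose within the 14-day limit, though the investigator may override that hold. Blood volume rises, which Section 2.5.1.5 asks centers to watch. Section 4.4.4 will bring additional 24-hour reports of CK elevation, including minor ones.

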3.4.2.10 Incidence of Toxicities

All Grade 3-5 toxicities according to CTCAE v5 occurring from randomization to Day 56 post-randomization will be described.

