4.4.4 Required Adverse Event Reporting

The required adverse event reporting for the BMT CTN 2002 protocol is outlined below.

- T-Guard arm: all adverse events, including SAEs, must be reported from randomization through 30 days following the last dose of T-Guard.
- Ruxolitinib arm: all adverse events, including SAEs, must be reported from randomization through Day 44 (to align with the maximum reporting period for participants in the T-Guard arm).
- Any SAEs occurring after that period, but assessed as related to the investigational product, must be reported.
- Any unanticipated SAEs from time of enrollment through the study defined follow-up are required to be reported..
- Any grade 4 anticipated event not collected on the calendar-driven toxicity or specified event-driven form must **also** be reported.
- Special Situations and Adverse Events of Special Interest (AESIs) must be reported from randomization through the study defined follow-up period.

- Grade 1 CMV infections, as defined in Appendix G, requiring treatment should be reported from randomization through the study defined follow-up period.

SAEs that require reporting will be reported through an expedited AE reporting system via the EDC system. **All SAEs, Special Situations, and AESIs must be reported within 24 hours of knowledge of the event.** Events entered in EDC will be reported using NCI's CTCAE Version 5.0. If there are network outages, a paper copy of the AE form must be completed and emailed to Emmes to initiate Sponsor review. Once the system is available, the event information must be entered into the system.

The Sponsor has a list of events classified as Special Situations. These events are 1) medication error, 2) overdose and 3) pregnancy. These events must be reported, regardless of grade or seriousness, following the reporting process for SAEs.

The Sponsor has a list of AESIs to be reported. These events include any grade of 1) TMA, 2) CRS, 3) CLS, 4) Myalgia, or 5) CK elevation and 6) grade 3 or higher cytopenias. These events must be reported, regardless of grade or seriousness, following the reporting process for SAEs.

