The operating characteristics of the truncated test are shown in [Table 5-4](#). They were obtained from a simulation study that assumed uniform accrual of 12 participants to the T-Guard arm during the run-in phase. During the run-in phase, this procedure rejects the null hypothesis in favor of the alternative 4.6% of the time when the true Day 30 mortality rate is 15% and 74.5% of the time when the rate is 45%. If the true Day 30 mortality rate is 45%, the DSMB will, on average, be consulted when 4 events have been observed in 9 T-Guard arm participants. The limited size of the run-in phase permits reliable detection only of a true mortality rate in excess of 40% but provides some assurance of the safety of T-Guard before proceeding with full enrollment.

Table 5-4: Operating Characteristics of the Binary SPRT for Single Arm Day 30 Overall Mortality Monitoring During Run-in Phase

True Day 30 Mortality Rate	15%	20%	25%	30%	35%	40%	45%	50%
Probability of Early Stopping	4.6%	11.4%	21.6%	34.5%	48.6%	62.3%	74.5%	84.1%
Mean # Deaths by Day 30	1.8	2.3	2.8	3.1	3.4	3.6	3.7	3.7
Mean # T-Guard Participants Enrolled	11.8	11.6	11.2	10.8	10.2	9.5	8.8	8.2

*Operating characteristics obtained from 100,000 Monte Carlo simulations

A second monitoring rule will evaluate whether the Day 60 mortality risk post-randomization for the T-Guard arm exceeds that for the ruxolitinib arm throughout the trial. Based on historical

data from the REACH trials and MAGIC, the expected probability of Day 60 mortality in Grade 3-4 SR-aGVHD participants is 40%, while a rate of 65% is considered to be unacceptable. The presence of excess Day 60 mortality risk in the T-Guard arm evaluated using an SPRT that compares a null odds ratio of 1 for Day 60 mortality risk under T-Guard vs. ruxolitinib to an alternative value of 2.79. The alternative odds ratio of 2.79 corresponds to the increase in risk produced if the ruxolitinib rate equals 40% as expected while the T-Guard mortality rate is higher at 65%. This rule will only consider early stopping to reject the null hypothesis of equal mortality risk. An aggressive rejection boundary will be used during the run-in phase in order to provide enhanced vigilance in comparing risk between arms, determined by nominal type I and II error rates of 20.5% and 25%, respectively. Following the run-in, the rejection boundary is determined by nominal type I and II error rates of 5% and 10%.

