5.6 ANALYSIS OF SECONDARY ENDPOINTS

The analysis of secondary endpoints will be based on the primary ITT analysis population. A supplemental analysis will also be performed in the PP population.

Key Secondary Endpoints:

The study has two key secondary endpoints: OS and DoCR. The comparison of OS between treatment arms will be alpha-protected; to protect the familywise type I error rate of 2.5%, a gatekeeping procedure will be employed where OS will be tested for superiority of T-Guard to ruxolitinib only if a significant benefit of T-Guard is found in the pivotal analysis of the primary endpoint.

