5.6.12 Incidence of Toxicities

The frequency of Grade 3-5 toxicities per CTCAE Version 5 occurring from randomization until 56 days post-randomization will be tabulated by organ system for each treatment arm. The maximum severity of reported toxicities during that period will also be summarized. The proportions of participants reporting Grade 3-5 toxicities through Day 56 will be compared between arms using logistic regression with adjustment for the stratification factors and for acute GVHD grade at randomization (Grade III vs. IV).

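### Grade 3 toxicity in participants who die after all-AE reporting stops but before the Day 56 toxicity record has no stated route into the Day 0-56 endpoint, and the gap is longer on T-Guard

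*Combined protocol and SAP*

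**What the plan says.** **Endpoint.** Section 3.4.2.10: "All Grade 3-5 toxicities according to CTCAE v5 occurring from randomization to Day 56 post-randomization will be described". Section 5.6.12 tabulates these events and adds a between-arm comparison: "The proportions of participants reporting Grade 3-5 toxicities through Day 56 will be compared between arms using logistic regression". Section 5.6 sets the denominator: "The analysis of secondary endpoints will be based on the primary ITT analysis population".

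**Toxicity record.** Section 4.3.2, item 12 of the post-randomization assessments: "Recording of toxicities on Days 56, 70, 90, and 180". No earlier toxicity record is scheduled, and none is tied to death or withdrawal.

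**AE reporting.** Section 4.4.4 requires on T-Guard that "all adverse events, including SAEs, must be reported from randomization through 30 days following the last dose of T-Guard". On ruxolitinib the same reporting runs to Day 44, chosen to match the longest possible T-Guard window. After that, what remains reportable is SAEs related to the product, unanticipated SAEs, AEs of special interest (AESIs, which include Grade 3 or higher cytopenias), and Grade 4 anticipated events not already on a form. Other anticipated events go onto calendar-driven forms, of which the toxicity form is one, or onto event-driven forms such as the death form.

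**Expected mortality.** Section 5.3.2 gives 15-20% at Day 30. For Day 60 it says: "the expected probability of Day 60 mortality in Grade 3-4 SR-aGVHD participants is 40%, while a rate of 65% is considered to be unacceptable".

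**Not stated.** Section 5.6.12 does not name the data source for the endpoint and has no rule for a participant who dies before Day 56. Section 5.6.11, on infections, treats death as a competing risk.

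**The concern.** A per-participant endpoint over 56 days needs some record of each participant up to Day 56 or death. Here two sources meet imperfectly. The AE log is complete early on but closes before Day 56. The toxicity form covers the rest but is filled in only at a visit that the participant must live to reach.

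Between the two, an anticipated, unrelated, non-AESI Grade 3 event in someone who dies before Day 56 is required by neither route. The interval is also not the same in the two arms. It opens at Day 36 for a T-Guard participant dosed on Days 0, 2, 4 and 6 (section 2.5.1.4), and at Day 30 for one who stops after a single Day 0 dose. It opens at Day 44 for everyone on ruxolitinib. Stopping T-Guard early because of toxicity therefore shortens the period of full reporting.

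The arms can thus differ in capture even when true toxicity and mortality are equal, and they do so in a population where early death is common. A record not made at the time is hard to recover at analysis.

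**Working it through.** **Check of the mortality input.** Section 5.3.2 derives an odds ratio of 2.79 from the 40% and 65% Day 60 rates: (0.65/0.35) / (0.40/0.60) = 2.786. This reproduces, so 40% is used below as the plan uses it.

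**Inputs from the plan**
- Mortality of 15-20% at Day 30 and 40% at Day 60 (5.3.2).
- T-Guard doses on Days 0, 2, 4 and 6 (2.5.1.4), so all-AE reporting closes on Day 6 + 30 = Day 36.
- Ruxolitinib all-AE reporting closes on Day 44 (4.4.4).
- 123 participants per arm (5.3.2).

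**Assumption.** The plan gives no mortality for Days 36, 44 or 56. I assume a constant hazard between Day 30 and Day 60, the same in both arms:

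S(t) = S(30) × [S(60)/S(30)]^((t−30)/30), with S(60) = 0.60.

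| | Day 30 mortality 15% | Day 30 mortality 20% |
|---|---|---|
| S(36) | 0.85 × (0.60/0.85)^(6/30) = 0.793 | 0.80 × (0.60/0.80)^(6/30) = 0.755 |
| S(44) | 0.85 × (0.60/0.85)^(14/30) = 0.722 | 0.80 × (0.60/0.80)^(14/30) = 0.699 |
| S(56) | 0.85 × (0.60/0.85)^(26/30) = 0.629 | 0.80 × (0.60/0.80)^(26/30) = 0.623 |
| Dead by Day 56 | 37.1% | 37.7% |
| Die Day 36-56 (T-Guard gap) | 16.4% | 13.2% |
| Die Day 44-56 (ruxolitinib gap) | 9.4% | 7.6% |

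**Other interpolations.** Linear interpolation, or one constant hazard from Day 0 to Day 60, gives 36.7-37.9% dead by Day 56. Over all three methods the gap is 11.5-16.7% on T-Guard (about 14-21 of 123) and 6.7-10.0% on ruxolitinib (about 8-12 of 123).

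**Deaths that all-AE reporting does cover.** Of deaths before Day 56, 55-70% occur by Day 36 and 73-82% by Day 44.

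**Misclassification if AE records feed the endpoint.** A participant is wrongly counted as free of toxicity only if they die in the gap and had no Grade 3-5 event recorded earlier. Table 1-3 reports that 78% of each REACH2 arm had a Grade 3 or higher AE by Day 28. Assuming that rate here, and that it is unrelated to death in the gap, 22% have no earlier event:
- T-Guard: 0.22 × 13-16% = 2.9-3.5%
- Ruxolitinib: 0.22 × 8-9% = 1.8-2.0%

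The difference is roughly 1 to 1.5 points. These are ceilings under those assumptions, because they take every such death to include an uncaptured Grade 3 event.

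**The case against.** The strongest objection is that the plan already collects most of this. All-AE reporting covers the majority of deaths before Day 56. AESIs, related or unanticipated SAEs and uncollected Grade 4 anticipated events are reportable beyond it. Infections are recorded through Day 180. Deaths are entered within 24 hours (4.3.1), and Grade 5 is a death related to an AE (4.4.2), so some deaths in the gap would themselves be endpoint events if the death form feeds the endpoint. The Form Submission Schedule cited in 4.4.4 is not among the documents and might add a form. Toxicity is also a secondary endpoint without alpha protection, and mortality is monitored separately.

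All of this stands, and it keeps the point small. It does not close the gap. The death form is not a toxicity record, the later rules leave out the class of Grade 3 event described above, and 5.6.12 does not say that any of these sources are used.

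A reader might go further and infer that toxicity is lost for all of the roughly 37% who die before Day 56, so that the arm with more deaths looks safer. That needs three things together: only the toxicity form is used, nothing is recorded for those who die, and they stay in the denominator as toxicity-free. On those terms, with 78% true toxicity in both arms, a constant hazard and Day 60 mortality of 50% on T-Guard against 40% on ruxolitinib, the observed rates would be 0.78 × 0.5^(56/60) = 41% and 0.78 × 0.6^(56/60) = 48%, an odds ratio of 0.74. With equal mortality it would be 1.0. The documents do not support this reading. Section 4.4.4 requires all AEs over most of the period, and nowhere are those who die said to count as toxicity-free. The plan is silent, which is a reason to clarify it and not evidence of that bias.

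**Conclusion.** The point holds as a gap in data collection that is cheap to close. The toxicity record starts at the end of the endpoint period, all-AE reporting stops before that, and the uncovered interval is longer on T-Guard than on ruxolitinib when dosing is on schedule. The two windows match only when T-Guard dosing runs to its 14-day limit.

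About 13-16% of the T-Guard arm and 8-9% of the ruxolitinib arm would die in the uncovered interval. If AE records count towards the endpoint, misclassification is at most about 3-3.5% against 2%. If only the toxicity form counts, it is larger, and its size depends on how deaths are handled.

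These figures rest on interpolated mortality taken as equal in both arms, T-Guard started on Day 0 with all four doses on schedule, and the REACH2 rate of 78% carried over to a Grade III-IV population.

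**What to change.** 1. In section 4.3.2 item 12 and Tables K-1 and K-2, make a toxicity record due at death or withdrawal before Day 56. It should cover the time since all-AE reporting ended for that participant, or since randomization if no AE record exists.
2. In section 5.6.12, state that AE and toxicity records are combined for the endpoint in both arms. State also that participants who die before Day 56 are classified from those records and are not counted as toxicity-free by default.

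**Cost.** One short form per early death or withdrawal. On the interpolation above, that is about 45-47 deaths per arm, of which some 14-21 on T-Guard and 8-12 on ruxolitinib fall in the uncovered interval. The two sources also need some reconciliation so that an event entered in both is counted once. No visit or procedure is added.

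Extra toxicity forms at Days 14 and 28 are not needed. On schedule, both days lie inside the all-AE window, so the forms would duplicate data already required and leave the gap untouched.
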